Study Protocol and results

**Internet based cognitive behavioural therapy for
depression in patients with Cardiovascular disease - The
DOHART Study**

NCT 02778074

Date: January 28 2019

Purpose and aims

Tailored internet-based cognitive behavioural therapy (I-CBT) is a new innovative and person-centred method that is promising that may be used to decrease depression in CVD patients. In patients with cardiovascular disease (CVD), depressive symptoms is a common co-morbidity leading to decreased wellbeing, and increased morbidity and mortality. Depressive symptoms are both underdiagnosed and undertreated in CVD patients. Earlier studies have demonstrated the efficiency of cognitive behavioural therapy (CBT) for many psychiatric conditions, but few studies have evaluated CBT in patients with CVD.

The purpose of this study is to evaluate the effects of the tailored I-CBT program on reducing depressive symptoms and other patient reported outcomes in patients with cardiovascular disease (CVD) and to explore factors related to implementation of the I-CBT program in clinical cardiac care.

Aims of the study

- To evaluate the effects of the tailored I-CBT depression program on depressive symptoms and quality of life.

Survey of the field

Background: The World Health Organisation (WHO) has estimated that CVD and depressive symptoms will in the near future become the two most common causes of disability.¹ Depressive symptoms, according to the WHO, produces greater decrements in health than other chronic physical diseases and a comorbid depression significantly worsens the health of patients with such diseases.²

In Europe, CVD is the major cause of hospital discharges and accounts for 43% of all deaths at all ages (i.e., > 4 million deaths annually).³ Depressive symptoms is highly prevalent in patients with CVD (20%–40%)⁴ and it significantly worsens the health of CVD patients. Depressed CVD patients experience poorer quality of life,⁵ more frequent rehospitalisation,⁶ higher healthcare costs and a shorter life expectancy than CVD patients without depression.⁶ Both biological and behavioural mechanisms can explain the negative effects of depressive symptoms in CVD. With regard to the biological mechanisms, our own and other studies have shown that depressive symptoms increases plasma levels of stress hormones and inflammatory activity, which may speed up the progression of atherosclerosis and impairment of cardiac function.^{4,7} Regarding behaviour, depressive symptoms can influence non-adherence to medication, development of a sedentary lifestyle and poorer self-care performance.^{4,8}

The WHO states that our ‘traditional care approaches’ such as primary care centres or outpatient clinics do not offer enough support or treatment to patients with a chronic disease and depressive symptoms, such as those with CVD.² The WHO emphasises that the implementation of interventions targeting depression in healthcare should thus be prioritised.² In line with this recommendation, our proposed study will contribute to the development, feasibility testing, and evaluation of the effectiveness of an internet-based cognitive behavioural therapy treatment program (I-CBT) aimed at treating depressive symptoms in CVD patients.

Rationale for the intervention: Why should CBT be chosen for this purpose? Antidepressant medication seem to have limited effect on depressive symptoms in CVD patients.⁴ Furthermore, adding anti-depressant to the existing complex medical treatment for CVD may be perceived as burdensome and also increase the risk of developing side effects. CVD

patients with depression prefer ‘talking’ therapies.⁹ There are other psychotherapies, but rarely, if ever, do they result in better outcomes than CBT.¹⁰ However, earlier studies of CBT in CVD patients’ only reports small effects on depressive symptoms. One probable reason is that most studies only used a single CBT component, such as psychoeducation alone, problem-solving therapy alone, relaxation alone or behavioural activation alone.¹¹ A program that combines different CBT components has been suggested to improve treatment efficacy.¹² Moreover, generic CBT programs may not be optimal for targeting depression in patients with chronic diseases since these programs are not adapted to the context of the disease,¹³ for example, by acknowledging the association between CVD and depression. We therefore believe that a CBT program that (I) includes different CBT components and (II) tailored to fit the context of CVD has the potential to improve the effect of CBT on depressive symptoms. This might also prevent the progression of CVD as well as improve quality of life and survival.

Project description

The study has the following research questions:

- What are the short- (nine weeks) effects of a nine-week I-CBT program on depressive symptoms and quality of life in patients with CVD and depressive symptoms.

Methods

Design of the study

The effects of the I-CBT program will be evaluated in a randomised controlled study (RCT).

Enrolment of study participants in the RCT

For the RCT study, 144 patients were recruited (Figure 1).

Power calculation: A recent published meta-analysis¹⁴ of studies evaluating the effect of internet based CBT on depression, that will be the primary outcome in the study, reported the effect size in studies including patients with depression to vary between 0.56-1.26 (mean 0.89), the mean number of patients in these studies was 107. Own power calculation: Effect size=0.5, alpha=0.05 (Z=1.96), Power 0.80 (Z -0.84) = 122 participants. Due to drop-outs or deaths the size of the study population for the RCT study was decided to n=140.

Step 1. Screening for participants. All CVD patients who received care at the department of cardiology the last 12 months in four hospitals in southeast of Sweden was contacted by a letter with information (n=11,992) about the study.

Step 2. Patients interested (n=272) in participating registered as interested on our website (www.dohart.se) for more information, registration and the provision of informed consent. After registration, the participants will respond to questions on the website (see figure 1). Inclusion or exclusion will be assessed by a board consisting of a cardiologist, a psychologist, a cardiology nurse specialists and a psychiatric nurse specialist.

[figure not shown]
Inclusion

- age > 18 years
- treatment for CVD according to European Society of Cardiology guidelines
- stable CVD (NYHA class I–III) and not having been hospitalised for CVD in the last four weeks.
- depressive symptoms (Patient Health Questionnaire-9¹⁵ (PHQ-9) > 5 points)

Exclusion

- severe CVD (NYHA IV) or another severe chronic life-threatening disease
- severe depression assessed as requiring acute treatment
- not being able to dedicate 3-4 hours to participate in the program
-

Figure 1. Description of the enrolment and randomisation of study participants

Step 3. Before final inclusion and randomisation, eligible participants was contacted for a telephone interview held by the psychiatric nurse specialist. Mini International Neuropsychiatric Interview (MINI) will be used to assess depression at this stage.

Step 4 The included (n=144) patients completed the baseline study questionnaires on our website and was then be randomised to nine weeks of internet-based CBT (n=72) or nine weeks in an web based discussion forum (n=72). As suggested by the ethical committee, those in the web-based discussion forum was offered I-CBT treatment after the termination of the study.

Theoretical underpinning for the CBT intervention

According to CBT theory¹⁶, depression arises from negative thoughts, emotions and behaviours that can be activated as a response to stressful life events, such as the development of CVD. Figure 2 shows a CBT model, inspired by Moorey¹⁷ of how CVD can cause depression. The inner circle of the model describes perceived losses, threats and stressful symptoms caused by CVD. This activate negative thoughts, emotions and behaviours, thus a process leading to development of depression (the outer circle). In the model, a vicious circle can be seen since the negative thoughts, emotions and behaviours in turn can worsen patients' perceived stress of CVD and thus both worsen depressive symptoms and CVD.

Intervention: With CBT the patients become active participants and perform exercises that enable them to become aware of, modify, as well as learn skills to cope with negative thoughts and unhelpful behaviours, which contributes to decrease negative emotions.¹⁶ CBT can help CVD patients to break the vicious circle. The nine-week tailored I-CBT program consists of the components of psychoeducation, relaxation, problem-solving and behavioural activation. Table 1 describes the I-CBT program and Figure 2 describes how the four components in the I-CBT will work to decrease depression. CBT usually includes some form of homework. Specifically, just seeing a therapist is insufficient, and change must be implemented in real life, which is achieved by collaborating with the patient and prescribing homework. The present I-CBT program thus also has homework assignments (Table 1) and the patients are provided with weekly feedback on them by a nurse specialising in mental health care who is supported by a psychologist and can consult with a cardiologist as well as a specialist cardiac nurse. Feedback is delivered in writing and focuses on positive aspects of the patient's progress; support is also provided to help the patients proceed with the program.

Figure 2. A CBT model describing how CVD can cause depression. The figure also describes how the 4 components in the I-CBT program (1) psychoeducation, (2) problem solving, (3) behavioural activation and (4) relaxation can help to decrease depression by modification of negative thoughts, behaviours and emotions.

[figure not shown]

Table 1. A brief overview of the I-CBT program

CBT component/Content	Aim	Homework
Week 1: Psychoeducation Introduction	Inform and engage the participant. Goal setting.	Identify values and set up goals for the participation in the program
Week 2: Psychoeducation Living with CVD	To understand what CVD is and its impact on life.	Self-assessment of CVD symptoms. Identification of situations when symptoms occurs. Propose coping strategies.
Week 3 Psychoeducation Depression and CVD	To understand what depression is and its link to CVD.	Identify symptoms of depression, fear and worries Identify situations when symptoms affects the participant.
Week 3: Relaxation	To learn relaxation	Practice relaxation continuously during the CBT program.
Week 4 and 5: Behavioural activation	To identify behaviours that have negative and positive impacts on wellbeing.	Mapping activities in a week schedule. Making a list of desirable activities. Planning and implementing new activities
Week 6 and 7: Behavioural activation	To reduce negative behaviours and increase positive ones.	Eliminate or reduce negative activities. Increase number of positive activities.
Week 8: Problem-solving	To identify perceived problems. To solve or cope with a problem.	Practicing problem solving in accordance to the problem solving tool
Week 9: Final module	Learn strategies to maintain the changes achieved.	Set up a personal strategy that can be used if depressive symptoms re-occur.

The control group participated in a web-based moderated discussion forum (i.e. ODF group) where new discussion topics were presented each week over a nine-week period. During participation in the ODF, no individual feedback was provided. However, participants could contact the moderator for support regarding how to use the ODF and for technical support. The topic was introduced without any extended background in a presentation consisting of statements and questions such as: What are the symptoms of CVD? Do you have any tips you would like to share on how you can handle the symptoms of CVD? How do you think that depressive symptoms and CVD affect the relationship between you and your significant others? Do you have any suggestions about how to handle problems related to feeling depressed or downhearted? The discussion took place in writing.

Measurements to evaluate the RCT

The PHQ-9¹⁵ will be used to measure the primary outcome (i.e. depressive symptoms). The PHQ-9 is a valid and frequently used depression questionnaire. To detect depression a sensitivity of 88% and a specificity of 88% has been reported in primary care patients¹⁸ whereas a sensitivity and specificity of 70 %r respectively 92% has been reported in patients with CVD.¹⁹ Table 2 gives an overview of the primary and secondary outcomes and the timing for measurements in the RCT.

Statistical analysis plan

Primary and secondary outcome data were checked for normal distribution by visual inspection or Q-Q plots. The primary analysis for comparison between groups (i.e. iCBT vs. ODF) was made on an intention-to-treat basis. Analysis of covariance (ANCOVA), which allows adjusting for baseline scores and regression to the mean was used for the comparison between groups. Missing data in the ANCOVA was imputed using last observation carried forward.

Table 2. The different measurements and the timing for measurements in the study.

	Questionnaires	Baseline	Post-CBT 9 weeks,
Primary outcome			
Depressive symptoms	Patient Health Questionnaire-9 ¹⁵	X	X
Secondary outcomes			
Depressive symptoms	Montgomery-Asberg Depression Scale	X	X
		X	X
Quality of life	Short Form-12 ²⁰	X	X
	Euro-QoL-5D ²¹	X	X

Results of the I-CBT program

Main results (Table 3) Compared to web-based discussion forum (ODF), iCBT had a significant and moderate treatment effect on the primary outcome depression (i.e. PHQ-9) (mean group difference -2.34 [95 % CI -3.58 to -1.10], $P < 0.001$, Cohen's $d = 0.62$). In the secondary outcomes, compared to ODF, iCBT had a significant and large effect on depression (i.e. MADRS-S) ($P < .001$, Cohen's $d = 0.86$) and a significant and moderate effect on the mental component scale of the SF-12 ($P < .001$, Cohen's $d = 0.66$) and the EQ-VAS ($P < .001$, Cohen's $d = 0.62$). A total of 60% ($n = 43$) of the iCBT group completed all seven modules, whereas 82% ($n = 59$) completed at least half of the modules. No patients were discontinued from the study due to high risk of suicide or deterioration in depression.

Table 2: Treatment effects for the primary and secondary outcomes. Data are mean (SD) unless otherwise stated.

	Internet-cognitive behavioural therapy ($n = 72$)		Online discussion forum ($n = 72$)		Mean between-group treatment difference, 95 % CI		P	Effect-size (d)
	Baseline	9 weeks	Baseline	9 weeks				
PHQ-9	10.71 (4.47)	6.63 (4.76)	10.22 (5.10)	8.68 (4.60)	-2.34	-3.58 to -1.10	<.001	0.62
MADRS-S	18.27 (6.98)	10.90 (7.45)	17.67 (6.19)	16.10 (7.93)	-5.58	-7.72 to -3.44	<.001	0.86
EQ-VAS	53.31 (20.03)	65.11 (21.81)	57.15 (18.10)	56.99 (22.08)	10.83	5.02 to 16.64	<.001	0.62
PCS12	39.70 (10.07)	41.84 (10.56)	37.63 (10.98)	37.80 (11.61)	2.46	-0.11 to 5.03	.06	0.32
MCS12	35.88 (9.22)	43.41 (11.04)	36.38 (10.02)	38.03 (10.52)	5.71	2.83 to 8.60	<.001	0.66

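### The stated 122 participants does not follow from the plan's own inputs, which require 126 (normal approximation) or 128 (t-test)

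*Combined protocol and SAP*

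**What the plan says.** The power calculation, under the heading on enrolment of study participants in the RCT, puts its inputs and its result in one statement: "Effect size=0.5, alpha=0.05 (Z=1.96), Power 0.80 (Z -0.84) = 122 participants". The next sentence builds the target on that result: "Due to drop-outs or deaths the size of the study population for the RCT study was decided to n=140". It gives no loss rate.

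The paragraph names no test, formula or software. It does not state sidedness in words, the allocation ratio or any baseline correlation. Allocation can be seen in Step 4, where patients were "randomised to nine weeks of internet-based CBT (n=72) or nine weeks in an web based discussion forum (n=72"). The statistical analysis plan section names the primary method: "Analysis of covariance (ANCOVA), which allows adjusting for baseline scores and regression to the mean was used for the comparison between groups".

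**The concern.** A sample-size statement that prints the effect size and both Z values can be checked by hand, and this one fails the check: the printed Z values contradict the printed total. If 122 is too low, it does not deliver the stated 80% power for the comparison that the inputs describe. The allowance for drop-outs and deaths, visible only as the gap between 122 and 140, also looks larger than it is. This sentence is the plan's only numerical justification for the size of the trial, so a reader should be able to reproduce it.

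**Working it through.** **Inputs**

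- Effect size d = 0.5, taken as exact (power calculation).
- Alpha 0.05 with Z = 1.96 (power calculation). This Z value implies a two-sided test.
- Power 0.80 with Z = 0.84 (power calculation). The value is printed with a dash or minus sign and is read as 0.84. Taken literally as negative, it would give 4 × (1.96 − 0.84)² / 0.25 = 20.07, which is not 122 either.
- Allocation 1:1, inferred from the 72/72 randomisation in Step 4.

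**Attempt to reproduce 122**

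Normal approximation, total N = 4 × (Zα + Zβ)² / d²:

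4 × (1.96 + 0.84)² / 0.5² = 4 × 7.84 / 0.25 = 125.44, or 62.72 per arm. Rounded up, this is 63 per arm and **126** in total.

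Two-sample t-test: 63.77 per arm, rounded up to 64 per arm and **128** in total.

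Against 122, these are 4 more patients (4/122 = 3.3%) and 6 more (6/122 = 4.9%).

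**Other readings of the same inputs**

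| Reading | Total N |
|---|---|
| One-sided test | 100 (normal), 102 (t-test) |
| One-sample comparison | 32 |
| Allocation 1.5:1 | about 133 |
| Allocation 2:1 | 144 |

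None gives 122.

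**Baseline adjustment**

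With d = 0.5 on the raw SD, ANCOVA multiplies N by (1 − ρ²), where ρ is the correlation between baseline and outcome. To reach 122 by the normal formula, ρ = √(1 − 122/125.44) = 0.166, or about 0.17. By the noncentral t with 119 degrees of freedom, ρ is about 0.21. The plan states no such value. Under the normal formula, ρ = 0.3 gives 116 and ρ = 0.5 gives 96.

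**A possible source**

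Using the power itself (0.80) in place of its Z value (0.84) gives 4 × (1.96 + 0.80)² / 0.25 = 121.88, which rounds up to 122. The documents do not show the working, so this remains a guess, and nothing here depends on it.

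**Power at d = 0.5, unadjusted, before losses**

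| Total N | Normal | t-test |
|---|---|---|
| 122 | 78.9% | 78.2% |
| 126 | 80.1% | 79.5% |
| 128 | 80.7% | 80.1% |
| 140 | 84.1% | 83.6% |
| 144 | 85.1% | 84.6% |

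The normal figure for 122 is Φ(0.5 × √(61/2) − 1.96) = Φ(0.801) = 78.9%. The effect size that 122 detects with 80% power is √(4 × 2.8² / 122) = 0.507 (normal), or 0.511 (t-test).

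**Margin up to 140**

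- From 122: 18 patients, 18/140 = 12.9%.
- From 126: 14 patients, 14/140 = 10.0%.
- From 128: 12 patients, 12/140 = 8.6%.

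**The case against.** Four points can be made for the plan.

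*Precision of the effect size.* It is printed to one decimal, and 0.507 or 0.511 would also print as 0.5. This is arithmetically true, but a planning value of 0.5 is naturally read as exactly 0.5, and nothing in the paragraph suggests that it was rounded.

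*The primary analysis is ANCOVA, so an unadjusted benchmark understates power.* This has force. The PHQ-9 confidence interval in the results table allows a rough check. Its half-width is 1.24, so the standard error is 1.24/1.977 = 0.627. With 72 per arm the residual SD is 0.627 × √36 = 3.76. The raw 9-week SD is √((4.76² + 4.60²)/2) = 4.68, so the implied correlation is √(1 − (3.76/4.68)²), about 0.59. With 0.5 on the raw SD, about 84 patients would then give 80% power, and 122 would give over 90%. This estimate is post hoc, comes from data imputed by last observation carried forward, and assumes that the interval is from the ANCOVA. It shows that the trial was probably not short of power. It does not explain 122, since such a correlation would lead to a much smaller number.

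*No decision turned on 122.* The target was 140 and 144 were randomised. This stands.

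*The loss margin is a weak argument.* The primary analysis is by intention to treat with last observation carried forward, so patients who drop out stay in the analysed number. This also stands, and no stated loss rate is breached because none is stated. Both of these last points limit the importance of the error; neither makes 122 correct.

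**Conclusion.** The figure is wrong as written. The plan's inputs require 126 (normal approximation) or 128 (t-test), not 122. This rests on an effect size of exactly 0.5, a two-sided test, 1:1 allocation and no baseline adjustment; the second and third are inferred from Z = 1.96 and the 72/72 split.

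The arithmetic is certain and the practical effect is small: 4 to 6 patients and 1.1 to 1.8 points of power. Enrolment and the reported results are untouched. The case for correcting it is that the sample-size statement should be reproducible, not that the trial was too small.

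**What to change.** Restate the requirement as 128 by t-test (126 by normal approximation), name the test, and add the loss that 140 was meant to cover; 140 allows 8.6% from 128 or 10.0% from 126.

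If 122 came from a baseline-adjusted calculation, say so and give the assumed correlation (about 0.17 by the normal formula, 0.21 t-based). If the sponsor prefers to keep 122 without that, the power should read about 78 to 79% and be labelled as applying to an unadjusted comparison, because the planned ANCOVA may well have more.

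The cost is one corrected sentence and one added clause. No further enrolment or re-analysis is needed. The visible margin up to 140 becomes 4 to 6 patients smaller.

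### With only baseline and week-9 measurements, LOCF in the primary ANCOVA gives every missing week-9 PHQ-9 zero change, which can bias the reported effect in either direction

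*Combined protocol and SAP*

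**What the plan says.** The statistical analysis plan sets the analysis population and model: "The primary analysis for comparison between groups (i.e. iCBT vs. ODF) was made on an intention-to-treat basis", using ANCOVA adjusted for the baseline score. The only missing-data rule is "Missing data in the ANCOVA was imputed using last observation carried forward". No assumption about why data are missing and no sensitivity analysis is given.

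The schedule is in the table headed "Table 2. The different measurements and the timing for measurements in the study". It has two time columns, baseline and post-CBT at 9 weeks, and no intermediate assessment of any outcome.

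The main results give the PHQ-9 comparison as "mean group difference -2.34 [95 % CI -3.58 to -1.10"], with d = 0.62, and the results table is headed with 72 patients in each arm. The power calculation expected some loss: "Due to drop-outs or deaths the size of the study population for the RCT study was decided to n=140", against a calculated requirement of 122.

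**The concern.** With two visits, last observation carried forward is baseline carried forward: a missing week-9 score is replaced by the pre-treatment score, so that patient's change is exactly zero. In a trial where both arms improve, this removes improvement from each arm in proportion to its loss. The group difference then depends on how much loss each arm had, even when loss is unrelated to outcome. Adjusting for baseline does not correct this.

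The rule is often defended as conservative. Here it need not be: heavier loss in ODF, or worsening among iCBT drop-outs, makes it favour iCBT. At stake is the size of the headline result, -2.34 points and the description of the effect as moderate.

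**Working it through.** **Inputs.** From the results table: PHQ-9 10.71 (SD 4.47) to 6.63 (4.76) in iCBT and 10.22 (5.10) to 8.68 (4.60) in ODF, 72 per arm; difference -2.34, CI -3.58 to -1.10. From the power calculation: allowance for loss (140 - 122)/140 = 12.9%. All loss rates below, including 12.9%, are assumptions, written as iCBT/ODF.

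**1. Reproducing the reported result.** The CI half-width is 1.24, so SE = 1.24/t(0.975, 141 df) = 0.627. Residual SD = 0.627 × √36 = 3.76, and d = 2.34/3.76 = 0.62. t = 3.73, P = 0.0003. These agree with the report. Changes are -4.08 and -1.54. The ANCOVA slope on baseline is (2.34 - 2.05)/0.49 = 0.59, where 2.05 is the raw week-9 difference and 0.49 the baseline difference.

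**2. Were 72 per arm analysed?** The SE implied by the table's SDs and slopes, for 72 per arm and for 63 (about 12.9% lost):

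| Outcome | n = 72 | n = 63 | From reported CI |
|---|---|---|---|
| PHQ-9 | 0.623 | 0.667 | 0.627 |
| MADRS-S | 1.082 | 1.157 | 1.082 |
| EQ-VAS | 2.91 | 3.12 | 2.94 |
| PCS12 | 1.285 | 1.375 | 1.300 |
| MCS12 | 1.458 | 1.559 | 1.459 |

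All five fit 72. Either missing scores were imputed or none were missing.

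**3. Direction under missing completely at random (MCAR).** With loss m in an arm, the LOCF change is (1 - m) × true change. LOCF exaggerates the difference when m_ODF × |true ODF change| > m_iCBT × |true iCBT change|. Substituting true change = reported change/(1 - m), this becomes an odds ratio of loss above 4.08/1.54 = 2.65. Break-even ODF loss is 12.2%, 22.7% and 31.9% for iCBT loss of 5%, 10% and 15%. Allowing for the 0.49-point baseline difference, the back-calculated value crosses -2.34 slightly earlier, at 10/21.3%.

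**4. Back-calculated observed-case difference.** Treat the table as LOCF output under MCAR. In each arm, change = reported change/(1 - m), slope = (0.59 - m)/(1 - m), and Var(Y) = [Var(LOCF) - m·Var(X) - m(1 - m)·change²]/(1 - m), where X is baseline and Y is week 9; the SE uses the observed n. At 12.9/12.9% the changes are -4.68 and -1.77 and the slope is 0.53. The difference is (-4.68 + 1.77) + 0.49 × (1 - 0.53) = -2.68, or -2.69 without intermediate rounding, with SE 0.663.

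| Loss | Difference (95% CI) |
|---|---|
| none | -2.34 (-3.58 to -1.10), as reported |
| 5/5% | -2.46 (-3.73 to -1.20) |
| 12.9/12.9% | -2.69 (-4.00 to -1.37) |
| 20/20% | -2.92 (-4.27 to -1.58) |
| 25/5% | -3.58 (-4.85 to -2.32) |
| 10/20% | -2.37 (-3.72 to -1.02) |
| 10/25% | -2.24 (-3.62 to -0.86) |
| 5/25% | -2.01 (-3.38 to -0.63) |

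For PCS12 (reported P = .06), P is .055 at 12.9/12.9% and .03 at 25/5%.

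**5. Simulation.** 20,000 trials, 72 per arm, baseline SD 4.8, slope 0.59, residual SD 3.76, changes -4.08 and -1.54, so the assumed truth is -2.54.

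| Loss | LOCF mean (coverage) | Step 3 formula |
|---|---|---|
| 12.9/12.9% | -2.21 (92%) | 0.871 × -2.54 = -2.21 |
| 25/5% | -1.59 (68%) | 0.75 × -4.08 + 0.95 × 1.54 = -1.60 |
| 5/25% | -2.72 (94%) | 0.95 × -4.08 + 0.75 × 1.54 = -2.72 |

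Observed-case ANCOVA gives -2.54 with 95% coverage. The low LOCF coverage comes from bias: at 12.9% its mean SE (0.621) matches its sampling SD (0.623), so there is no separate error in the interval.

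**6. Loss related to outcome.** At 12.9/12.9% with iCBT drop-outs ending 2 points above baseline, the truth is -1.76. LOCF gives -2.22 (coverage 88%) and observed-case ANCOVA -2.55 (78%). Both overstate the effect, observed-case by more.

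**7. Type I error** when both arms improve equally by 1.5 to 3 points: 5.0% at 10/10%, 5.9–7.8% at 10/20%, 7.9–16.9% at 5/25%.

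**The case against.** The strongest reply is that nothing in the text shows that any score was missing. The counts may be in the figure captioned "Figure 1. Description of the enrolment and randomisation of study participants", which was not available here. At 5/5% the estimate moves by only 0.12 points. The 12.9% is a recruitment margin covering drop-outs and deaths, not a forecast of missing questionnaires, and 144 patients were enrolled rather than 140. All of this stands. It limits what can be said about size, but it does not change what the rule does to a missing score.

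Second, exaggeration under MCAR needs much heavier loss in ODF, and no passage suggests that. Indirect facts lean the other way: ODF patients were offered I-CBT afterwards, and 40% of iCBT patients did not finish all modules. That is fair, although incentive and adherence are not follow-up. No patient was discontinued for deteriorating depression, but that does not cover patients who simply stopped responding.

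Third, a missing-at-random analysis can be worse than LOCF, as step 6 shows. At 12.9% per arm, with ODF drop-outs like completers, LOCF centres on -2.21 and observed-case on -2.54, midpoint -2.375. LOCF is therefore closer when 0.129 × (4.08 - improvement of iCBT drop-outs) exceeds 0.165, that is, when they improve by less than about 2.8 points. This stands too. It is the reason for a delta-adjusted analysis and for using module completion, and no reason to rely on LOCF alone.

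The Type I error figures illustrate the mechanism; they do not undermine the reported significance.

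**Conclusion.** The concern holds. Under this schedule LOCF means zero change for every missing score, and the resulting bias can go either way. Over the MCAR loss patterns tried, the observed-case PHQ-9 difference behind the reported -2.34 ranges from -2.01 to -3.58, and every interval excludes zero. The conclusion that iCBT reduces PHQ-9 more than ODF is not challenged on this ground; the size of the effect is.

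These figures rest on assumed loss rates, on the results table being LOCF output, and on loss being completely at random except in step 6. The actual size and direction are unknown, and the bias is zero if no week-9 score was missing. This should be fixed; confidence in the mechanism is high.

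**What to change.** Re-analyse the data already held under missing at random, in one of two ways:

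- a likelihood-based model with baseline and week 9 both as outcomes, a common baseline mean, an arm-by-time effect and unstructured covariance; or
- multiple imputation by arm from the baseline PHQ-9, MADRS-S, SF-12 and EQ-5D scores, followed by the same ANCOVA.

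Modules completed can be added as an imputation predictor within iCBT. This helps when poor engagement drives both loss and outcome. In a simulation (1,500 trials, 20 imputations, truth -2.54), 13 of 72 iCBT patients completed less than half the modules. They had an assumed 50% loss and change of -1.0, against 4.8% and -4.76 for the rest, with 12.9% loss in ODF. Imputation without modules gave -2.81 (coverage 93%), with modules -2.52 (95%), and LOCF -2.45 (94%). Only the 13/72 split comes from the documents.

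Base the stated effect size on the new analysis, labelled post hoc, and keep the LOCF estimate visible as the analysis originally stated. Add a delta-adjusted sensitivity analysis that shifts missing scores in each arm separately, and say how any deaths are handled. Give the observed week-9 n per arm beside the estimates if the enrolment figure does not already do so. If nothing was missing, those counts settle the matter.

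The cost is a change of SAP wording, one re-analysis, a post hoc label, and a CI about 3% to 15% wider at 5% to 20% missing per arm (observed-case to LOCF SE ratio 1.03, 1.09 and 1.15 at 5%, 12.9% and 20%). The new estimate can overstate the effect if iCBT drop-outs did worse than the model predicts, so the delta analysis is a necessary part of the change.

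### Does the report of no discontinuations for suicide risk or worsening depression need a defined event and a detection procedure behind it?

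*Combined protocol and SAP*

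**What the plan says.** Under Results of the I-CBT program (Main results), the document reports: "No patients were discontinued from the study due to high risk of suicide or deterioration in depression". It is the only mention of suicide in the document.

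The methods touch the subject in these places:

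- **Before randomisation.** The exclusion list includes "severe depression assessed as requiring acute treatment". For the telephone interview in Step 3, it says the "Mini International Neuropsychiatric Interview (MINI) will be used to assess depression at this stage".
- **During treatment, iCBT arm.** The Intervention section provides "weekly feedback on them by a nurse specialising in mental health care who is supported by a psychologist", where the feedback is on homework and is given in writing. It adds that "support is also provided to help the patients proceed with the program".
- **During treatment, control arm.** The discussion forum (ODF) was moderated. "During participation in the ODF, no individual feedback was provided", and the moderator could be contacted about using the forum and for technical help.
- **Scheduled measurement.** The timing table in the Statistical analysis plan has PHQ-9 and the Montgomery-Asberg scale at baseline and at 9 weeks, with nothing between.

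The results also say that 60% (n = 43) "of the iCBT group completed all seven modules", and that 82% (n = 59) completed at least half of the modules.

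**The concern.** A reader may take the sentence as a safety finding and look for the method behind it. None is stated. The severity exclusion and the MINI interview both come before randomisation. The week-9 questionnaires arrive as treatment ends, so they could not have prompted a discontinuation during it. In between, the iCBT arm had a mental health nurse reading homework each week, while the control arm had no individual feedback. If detection differed, iCBT was plausibly the better observed arm. Its observation may not have been complete either, since some patients did not finish the modules and the document does not say whether contact with them continued.

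The zero could then mean that these events were looked for and not found, or only that none came to the trial team's attention. This matters somewhat because the purpose includes the wish "to explore factors related to implementation of the I-CBT program in clinical cardiac care", and this is the one sentence that speaks directly about harm.

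**Working it through.** **1. Can the zero be reproduced?** No. The document gives no event definition, denominator, split by arm or assessment schedule for it. The only usable denominators are those in Step 4: 72 + 72 = 144 randomised.

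**2. What the zero would mean as a rate, with complete detection.** The exact two-sided 95% upper limit for 0 of n is 1 - 0.025^(1/n).

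- Whole study: 1 - 0.025^(1/144) = 0.0253, or 2.5%.
- One arm: 1 - 0.025^(1/72) = 0.0499, or 5.0%.

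**3. With incomplete detection.** Let s be the chance that a patient with the event was both identified and discontinued. The document does not give s, so these values are assumptions. The limit is approximately the figure in step 2 divided by s.

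| s (assumed) | 0 of 144 | 0 of 72 |
|---|---|---|
| 1 | 2.5% | 5.0% |
| 0.75 | 3.4% | 6.7% |
| 0.5 | 5.1% | 10.0% |
| 0.25 | 10.1% | 20.0% |
| 0.1 | 25.3% | 49.9% |

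The spread comes entirely from s. It also mixes two things: a patient who was identified but kept in the study counts as a miss. The table shows why the zero should not be turned into a rate. It does not show an error, because the document makes no such conversion.

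**4. Module completion.** 72 - 43 = 29 patients (40%) did not complete all modules, and 72 - 59 = 13 (18%) completed fewer than half. The document does not say that contact with them was lost, so unobserved iCBT patients are a conjecture.

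**5. Does the zero conceal worsening that the data show?** Week-9 symptom worsening is a different quantity, but it can be approximated for PHQ-9 from the results table.

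- SE from the CI, with t on 141 df: (3.58 - 1.10)/2 divided by t = 0.627.
- Residual SD: 0.627/√(2/72) = 3.76. Check: 2.34/3.76 = 0.62, which reproduces the reported Cohen's d.
- Pooled week-9 SD: √((4.76² + 4.60²)/2) = 4.68.
- Implied baseline to week-9 correlation: √(1 - (3.76/4.68)²), about 0.59.
- Mean change: ODF 8.68 - 10.22 = -1.54; iCBT 6.63 - 10.71 = -4.08.
- SD of change, √(SD₀² + SD₉² - 2r·SD₀·SD₉): ODF 4.39; iCBT 4.16.
- Rise of 5 points or more (illustrative cut-off, not in the document; normal approximation with continuity correction): ODF 1 - Φ((4.5 + 1.54)/4.39) = 8.4%, about 6 of 72; iCBT 1 - Φ((4.5 + 4.08)/4.16) = 2.0%, about 1 of 72.
- For r from 0.4 to 0.7, the range is 5.5% to 12.9% in ODF and 0.8% to 4.5% in iCBT.

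Some patients in both arms probably scored higher at week 9, with more of them among controls. That is compatible with no discontinuations, and it does not suggest hidden harm from iCBT. These are approximations from summary data. The SDs may include values carried forward, and with two time points such values enter as zero change.

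**The case for a change.** The best case for a change is that this is a trial in patients selected for depressive symptoms, and one sentence carries the direct safety message. The methods that would let a reader weigh it are absent, and observation was plausibly unequal between arms. The remedy would cost a few lines from trial records: the definitions used, who could identify the events in each arm and when, or a plain admission that there was no systematic check. A post hoc display of observed week-9 change by arm, without carried-forward values, would use data already held.

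The textual part of this stands: neither event is defined, and no procedure for identifying it during treatment is stated. The reading advice also stands, that the zero is a count of decisions.

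Three parts are weaker. First, it goes too far to say there was no way of identifying these events. A nurse reviewed homework weekly, and in week 3 (Table 1) that homework asks patients to identify their depressive symptoms. The forum was moderated, and both depression scales were collected in both arms at week 9. Second, the harm information is not confined to one sentence, since the results table gives PHQ-9 and MADRS-S by arm at both times. Third, the stated purpose is to explore factors related to implementation, and the research question covers depressive symptoms and quality of life only.

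The argument from silence also needs some caution. Figure 1 is not shown, although its caption concerns enrolment and randomisation.

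**Conclusion.** No change is called for. The gap in the description is real, but the sentence is a statement of patient disposition. It is not shown to be false, and the document derives no rate, comparison or safety conclusion from it. The document already carries the results, so writing out definitions now could not alter what was observed. Nor would it correct any stated rule, number or conclusion. A table of week-9 change would be an addition to the reporting and would repair nothing. The efficacy estimate is untouched.

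Readers should take the zero as the number of discontinuation decisions, and not as evidence that no patient worsened. Anyone who wants a limit can use 2.5% for 0 of 144 or 5.0% for 0 of 72. Both are two-sided 95% upper limits and both assume complete detection, which the document neither claims nor supports. Wider limits rest on an assumed detection probability and are not findings about this trial. The conclusion rests on the sentence being used only as it is here; quoting it as a safety rate would need the missing definitions and detection method.
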